Please note, the primary outcome of interest is CD4 count, which will be collected with a review of participants' medical records following each study visit. Participants' viral load and current antiretroviral therapy regimen will also be extracted from participants' medical records following each study visit. Other measures will be in the REDCap questionnaires that will be administered using iPads.

B. Description of Populations to be Enrolled:

Individual interviews to adapt infographics to the Latino population of Denver, CO
Patient participants for interviews to identify necessary changes to infographics will be adults (≥ 18 years), Hispanic/Latino, English or Spanish-speaking, and living with HIV. If patient participants are pregnant, they may still be included.

RCT - Interventionists

Inclusion criteria for clinicians who will administer the intervention during the RCT will be those who have offered HIV-related care for greater than one year and are not planning to leave the clinic for the next year.

RCT - Patient participants

Inclusion criteria for patient participants for the RCT will be that patients are adult (≥ 18 years), Hispanic/Latino, English or Spanish-speaking, living with HIV with a detectable viral load (>30 or >40 copies/mL depending on the laboratory test) at any point in the past year or be newly diagnosed with HIV, or have an indication of adherence risk as identified by their provider and be planning to receive care at the study site for the next year. If patient participants are pregnant, they may still be included in the study. Participants from the US site are expected to reflect the demographics of Latino patients at the Center for Positive Health (CPH), who are predominantly male (85%) and Mexican (90%). Participants from the DR will reflect the population at CFLR, which is majority female (57%) and Dominican (81%).

Key-stakeholders who participate in in-depth interviews

Key-stakeholders for in-depth interviews to assess implementation factors of incorporating the SMART on FHIR app into electronic health records will be clinicians or other employees at both sites who provide HIV-related education to patients, have been working in HIV care for greater than one year, and interact with the electronic health record at their site on no less than a weekly basis.

Usability testing of Creole version of the mobile app

Table 1. Outcome measures	
Outcome	Measure
Proximal Outcomes	

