At the DR site, the RA will notify clinic staff of eligible participants at the beginning of each recruitment day. Then, when an eligible participant presents to the clinic for their regularly scheduled appointment, initial contact will be made by clinic staff (face to face) who will introduce the study by providing a brief description of the study using the approved recruitment script and will then introduce interested participants to the RA, who will further explain the study, confirm eligibility, and complete informed consent and randomization.

At the US site, the RA will identify eligible participants for recruitment days the day before. Then, the RA will call eligible participants to confirm eligibility and explain the study by providing a brief description using the approved recruitment script. If a potential participant is interested, they will be invited to come to the clinic an hour before their scheduled appointment to complete the study visit. When a participant presents to the clinic, the RA will further explain the study, confirm eligibility, and complete informed consent and randomization. If the baseline/enrollment visit will be completed virtually, the procedures for recruitment/enrollment will be exactly the same, they will just be conducted over the phone

Table 2. Study activities at each visit in the RCT

Time point	Activity and group (Treatment (Tx), Control (Cl), or Both)
Baseline	
• Randomization• Baseline assessment (Both)• Standard Care (Cl)• Exposure to intervention (Tx)
3 months	
• Standard Care (Cl)• Exposure to intervention (Tx)• Follow-up assessment (Both)
6 months	
• Standard Care (Cl)• Exposure to intervention (Tx)• Follow-up assessment (Both)• In-depth interviews with PWH begin (Both)
9 months	
• Follow up assessment (Both)
Study end	
• Follow-up interviews for interventionists (5 per site)• In-depth interviews with key stakeholders (15 per site)

or via a HIPAA compliant platform such as Skype or Zoom. During virtual enrollment visits, the RA will complete informed consent electronically through REDCap.

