Permuted block randomization stratified by clinical site will be computer generated a priori and placed in ordered opaque envelopes by a study team member who is not recruiting; thus, group assignments will be blind to the study team.⁶¹ Procedures will then take place as described in Table 2.

Time intervals of study visits (baseline, 3-, 6-, and 9-months) were selected as CD4 count and viral load may change at three months after ART initiation.⁶² Study participants will have visits with interventionists (treatment group) or other providers (control group). Prior to the study, standard education at each site will be evaluated to ensure the only difference between treatment and control groups is the infographic intervention. The intervention will not be administered at 9-month visits to enable assessment of long-term effects. No extra time will be allowed for intervention study visits and participants will be reminded of visits via phone. Half of intervention visits (randomly selected) will be audio recorded and a checklist of intervention components will be independently completed by two study team members, then compared to verify intervention fidelity.

In-depth interviews with key stakeholders

Semi-structured individual interviews will be conducted with up to 15 clinicians at each site who provide patient education to establish preferences and recommendations for integrating the app into each EHR (Aim 3). Interview guides will be rigorously developed⁶³ and questions will be guided with a theoretical model.⁶⁴

Usability testing of Creole version of the mobile application

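### As written, randomisation comes before the baseline questionnaire, so the self-reported secondary outcomes get a baseline that allocation could affect; take those scales before the envelope is opened.

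*Combined protocol and SAP*

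**What the plan says.** Section IV.C (RCT study procedures) has the research assistant "confirm eligibility, and complete informed consent and randomization" in one step, at both the DR and US sites, with no questionnaire named before it. Virtual enrolment is not an exception: "If the baseline/enrollment visit will be completed virtually, the procedures for recruitment/enrollment will be exactly the same". After describing the opaque envelopes, the same section says "Procedures will then take place as described in Table 2".

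In Table 2 the baseline row opens "Randomization• Baseline assessment (Both", followed by standard care or the intervention. The 3- and 6-month rows reverse care and assessment: "Exposure to intervention (Tx)• Follow-up assessment (Both".

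On masking, the envelope sentence ends "thus, group assignments will be blind to the study team". Allocation then determines who the participant sees: "Study participants will have visits with interventionists (treatment group) or other providers (control group".

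Section IV.A takes CD4 count, viral load and ART regimen from medical records; "Other measures will be in the REDCap questionnaires that will be administered using iPads". Section IV.D.2.2 puts every outcome not taken from records into the baseline assessment. The Potential Risks text says that questionnaires are completed with a study team member. Under Secondary Analyses in section IV.F, the four-visit mixed-model plan is repeated for these outcomes, and a simpler model compares the arms at 9 months with baseline as a covariate.

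**The concern.** Baseline enters the analysis of the self-reported outcomes twice: as one of four repeated measures and as the adjusting covariate at 9 months. Both uses rest on baseline being unrelated to arm except by chance. Randomisation guarantees that for a value recorded before allocation, but not for one recorded afterwards. A participant who expects the new approach, or is disappointed at missing it, may answer questions on engagement, satisfaction or self-efficacy differently, and a study team member who knows the arm may influence the session. Adjusting for baseline cannot repair this, because baseline is the value at risk.

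The point is confined to self-reported scales. Laboratory values come from records. Information recall is a knowledge test and not obviously open to this route. The source of the medication possession ratio is not stated, so it is left out.

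**Working it through.** **The order.** Three places agree: the recruitment text (consent and randomisation together), the sentence sending the reader on to Table 2, and the baseline row of that table. Table 2 does not label its bullets as a sequence. However, assessment stands before care at baseline and after care at months 3 and 6, which suggests that the order is meant. No place in the documents puts the questionnaire ahead of randomisation.

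**Plan figures used.** The sample size reproduces: N = 4(1.96 + 0.84)²(1 + 3ρ)/(4 × 0.45²) gives 67.8, 96.9 and 126.0 at ρ = 0.25, 0.50 and 0.75, against 68, 97 and 126 in Table 3. The illustration uses the plan's ρ = 0.75 and 126/2 = 63 per arm.

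**Assumptions, not in the documents.** Knowing the arm shifts the treatment-minus-control difference by d0 SD at baseline and by d1 SD at each of months 3, 6 and 9. There is no true effect, the correlation is exchangeable, and there is no random slope.

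**Bias, in SD**
- Time-averaged difference: (d0 + 3d1)/4.
- Treatment-by-time over 9 months: weights 9(t − 4.5)/45 = −0.9, −0.3, 0.3, 0.9, giving 0.9(d1 − d0).
- Baseline-adjusted 9-month difference: d1 − ρd0.

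**Standard errors at ρ = 0.75**
- Time-averaged: √(2/63 × (1 + 3ρ)/4) = 0.161.
- Treatment-by-time: √(2/63 × 1.8(1 − ρ)) = 0.120.
- 9-month: √(2/63 × (1 − ρ²)) = 0.118.

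Rejection rate = Φ(−1.96 + b/SE) + Φ(−1.96 − b/SE), where b is the bias. Re-ordering sets d0 = 0.

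| Scenario (ρ = 0.75) | Time-averaged | Treatment-by-time | 9-month |
|---|---|---|---|
| Baseline only (d0 = 0.10, d1 = 0), as written | +0.025; 5.3% | −0.09; 11.7% | −0.075; 9.8% |
| Same, re-ordered | 0; 5.0% | 0; 5.0% | 0; 5.0% |
| Half persists (d1 = 0.05), as written | +0.0625 | −0.045 | −0.025 |
| Same, re-ordered | +0.0375 | +0.045 | +0.05 |
| Fully persists (d1 = 0.10), as written | +0.10; 9.5% | 0; 5.0% | +0.025; 5.5% |
| Same, re-ordered | +0.075; 7.5% | +0.09; 11.7% | +0.10; 13.6% |

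At ρ = 0.25 the baseline-only rates as written are 5.5%, 7.2% and 5.2%. Signs reverse if the shift is negative. The figures apply to continuous scales, not to the dichotomous SMAQ or the ordinal health status score. The plan's random slopes would widen the treatment-by-time standard error, so those rates are upper limits for the stated shift.

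**The case against.** The strongest objection is that harm needs three things: the envelope opened before the questionnaire, someone in the session aware of the arm, and answers moved by that knowledge. Only the order is documented, and part of that is inferred from a bulleted list. This stands. A reader might infer that participants know their arm while completing the baseline scales, but the documents do not say when the arm is disclosed. Equally, the sentence on blinding of the study team does not settle it the other way. It is drawn as a consequence of the sealed envelopes, so it covers concealment until opening, and nothing extends it beyond that.

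A second objection is that re-ordering may not help. This also stands in part. When the shift half persists, the treatment-by-time bias keeps its size and the 9-month bias doubles; when it fully persists, both rise. The present order looks better there only because two unknown shifts happen to offset each other, which is no reason to keep it. Nor does re-ordering guarantee that the remaining bias has the same sign everywhere. With d0 = 0 and an assumed waning shift of 0.10, 0.05 and 0, the time-averaged bias is 0.15/4 = +0.0375, but treatment-by-time is −0.3 × 0.10 + 0.3 × 0.05 = −0.015.

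Third, the version is dated September 2023 and the trial was planned to start in January 2021, so enrolment may be over. The documents do not say; the fix allows for both cases.

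**Conclusion.** The point holds as a cheap improvement to the secondary analyses. As documented, self-reported outcomes are measured at baseline after allocation, with no stated safeguard against knowledge of the arm. That bias occurs is not shown, and every shift size here is an assumption. For a 0.10 SD shift at baseline alone, false rejection at ρ = 0.75 is between 5.3% and 11.7%, depending on the analysis. The case for change is a baseline that allocation cannot affect, not a guaranteed fall in net bias.

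A reader might infer that the primary result is threatened. The documents do not support that: CD4 count comes from records, and the 126 evaluable and 164 randomised participants are unchanged. Confidence is medium, because actual practice may already differ from the text.

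**What to change.** (a) In the recruitment text of section IV.C and in Table 2, state that the baseline questionnaire is completed after consent and before the envelope is opened, at both sites, in person and virtually. If time is short, put at least the self-reported outcome scales first; demographics, SAHL, NVS and SASH can follow allocation.

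(b) If enrolment has closed, report the order actually used and who knew the arm during the questionnaire. For these outcomes, add a sensitivity analysis of months 3, 6 and 9 without baseline. It carries no baseline shift, though any follow-up shift remains.

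**Cost.** No new data and no change in sample size. Under (a), allocation comes later in the visit. The US site has one hour before the appointment for the whole study visit, and the DR site, which approaches people as they arrive, has no stated window. Because arm decides the provider, later allocation could add to the wrong-provider scheduling that section IV.E already warns of. Under intent-to-treat that would dilute the contrast between arms, including the CD4 contrast. This is why the outcome-scales-first option is offered.

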COMIRB Protocol

COLORADO MULTIPLE INSTITUTIONAL REVIEW BOARD
[name] [contact] [contact]

Protocol #: 20-0163

Project Title: Information Visualizations to Enhance HIV-Related Communication in Diverse Clinical Settings

Principal Investigator: [name]

Version Date: September 20, 2023

I. Hypotheses and Specific Aims:

Brief background

In preliminary studies, the PI developed and evaluated a set of HIV-related infographics to improve clinician-patient communication and patient outcomes among Latino persons living with HIV (PWH). This work was conducted in the Dominican Republic (DR) and in New York City. Simultaneously, the PI developed a Substitutable Medical Applications and Reusable Technology (SMART)® application (app) compatible with the Fast Healthcare Interoperability Resources (FHIR)®, which is the standard for connecting mobile apps and electronic health records. She has incorporated her evidence-based infographics into this app so her intervention can be scaled up to reach clinicians and their Latino patients living with HIV globally. The next steps in this work are to increase generalizability of the intervention by adapting it to an additional Latino group (persons of predominantly Mexican descent) and to test the efficacy of the intervention to improve clinician-patient communication and health outcomes.

The aims of this study are therefore to:

Aim 1 Adapt previously designed and evaluated infographics for relevance to persons with HIV (PWH) of predominantly Mexican descent through individual interviews and incorporate final infographics into the mobile app prior to the proposed RCT.

Aim 2 Conduct a multi-site randomized controlled trial to assess the efficacy of the intervention (infographics administered through a mobile app) as compared to standard care in improving treatment outcomes (CD4 count, viral load, self-efficacy to manage HIV, among others) of Latino PWH and determine how resultant effects vary over time (baseline to 9-months) and between sites (DR and CO).

Aim 3 Assess implementation factors of integrating the SMART on FHIR app into EHRs through in-depth interviews and leverage findings to ensure the app effectively interfaces with EHRs in the CO and the DR.

Complementary to this work, a better understanding of how distinct Latino groups perceive HIV infection and prefer to communicate regarding HIV is needed so interventions can be modified accordingly. Thus, the last aim of this study is exploratory.

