Therapeutic communication methods, such as motivational interviewing (MI), targeted at HIV self-management behaviors can help clinicians influence behavior change.^{29,30} During MI, specific techniques such as reflective listening and asking open-ended questions are used to emphasize collaboration and acceptance.²⁹ Incorporating targeted training in this method, even if it is brief,^{29,31,32} into interventions enables providers to deliver health education messages that promote healthier behaviors.^{29,33} The proposed intervention includes a brief training in MI, so clinicians can more effectively provide information to PWH.

The integration of evidence-based infographics into EHRs will enable infographics to be easily accessible and efficiently scaled up for use at clinical sites locally and globally. The applicant's previously designed and tested infographics are now automated in a Substitutable Medical Applications and Reusable Technology (SMART)[®] Application (app) compatible with the Fast Healthcare Interoperability Resources (FHIR)[®].³⁴ This is the standard for communicating between apps and electronic health records (EHR) via an application programming interface (API).³⁴ The resultant app will enable providers to access evidence-based infographics to facilitate HIV-related communication at a large scale. Unfortunately, electronic health tools, and their advantages, are more widely available in developed settings.³⁵⁻³⁷ But, a recent push to develop open-source electronic health records in low and middle income countries will enable FHIR compatible devices to be accessible to those living in limited-resource settings.³⁸⁻⁴⁰ The proposed study will leverage this advancement and provide a valuable platform and guide through which other researchers and developers can expand technologies to meet the needs of organizations and populations in limited-resource settings globally.

Understanding if infographics are acceptable to non-Latino populations is an important step towards generalizability and future scalability of this intervention.

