Intervention infographics are available in English and in Spanish and were created using a rigorous iterative design process.⁴⁶ They are intended to assist clinicians deliver patient education through culturally appropriate and visually appealing representations of key HIV-related concepts, systematically identified in a preliminary study.⁴⁷ For the trial, up to five clinicians at each site will be selected to use infographics. These “interventionists” will first attend a training, held by the study team, on how to use infographics to guide education using motivational interviewing (MI),³⁰ the mobile health application that contains the infographics, and on how to maintain intervention fidelity.^{59,60} During training, key concepts of infographics and MI will be reviewed then attendees will conduct “mock visits” to review learned components of MI, the mobile application and infographic content, confirm understanding of study procedures, and ensure interventionists uniformly administer the intervention. Additional training sessions will be held during the study to reinforce interventionists’ ability to implement learned skills. Also, during the second training session, interventionists will complete a questionnaire (the system usability scale (SUS)) to assess usability of the mobile health app containing infographics. During the study, in normal clinic visits, interventionists will use MI and infographics to guide education with participants using the infographics that will appear in the app, easily accessible on iPads. If a provider is conducting a telehealth visit with a study participant in the treatment group, during times of COVID-19 surges or for any other reason, they will have paper copies of the infographics to show participants during video visits.

RCT study procedures

During recruitment, clinic staff at each site will work closely with the Research Assistants (RA) to identify eligible participants on or before each recruitment day by verifying eligibility criteria in the electronic health records (EHR).

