
The study team will strictly adhere to the procedures detailed in this protocol, including methods to mitigate risks to participants.

Justification of procedures

Because this study involves no more than minimal risks to participants, the above described procedures and data collection techniques are justified as they are all necessary to satisfy the research aims of this study. Additionally, having the option to complete visits virtually or in-person will ensure maximum safety for patients and providers in times of COVID-19 surges.

E. Potential Scientific Problems

As attrition may be a concern in hard to reach populations,⁶⁹ we accounted for 22% attrition in our sample size calculations. To encourage retention, as was successful in the K99 trial in the DR, participants will be reminded of visits via phone calls prior to study visits and incentives appropriate for each site will be provided. Recruitment will be monitored to ensure a sufficient pace of enrollment and timelines will be extended if needed.

Intervention fidelity and contamination are concerns as participants may be scheduled to see the incorrect provider, providers may use infographics with control group participants, or simply may not use infographics. Intervention fidelity will be assessed by providers, patients, and a study team member, and contamination addressed with intent-to-treat analysis.

F. Data Analysis Plan

Sample size calculations

Individual interviews

Up to 15 participants will participate in individual interviews. This sample size was established as 15 participants are likely to be able to identify 90% of usability concerns in informatics-based studies⁷⁰ and as few as 10 are likely to achieve saturation in qualitative studies on specific themes (e.g. the experience of living with HIV) with relatively homogenous samples (e.g. Latino persons of predominantly Mexican origin/descent living in Denver, CO).⁷¹

RCT – Interventionists

Up to 5 interventionists at each site will be purposefully selected to participate. This sample size is based on preliminary feasibility studies.

RCT – patient participants (n=164, 82 at each site, 41 per group)

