HIV continues to be a global concern, but the focus on HIV treatment and research have shifted from considering HIV to be a devastating acute condition to a chronic condition that is manageable with optimal self-management and treatment adherence. This shift in attention and disease progression requires persons living with HIV to effectively manage their health for long periods of time. However, individuals with limited health literacy may have difficulty accessing and using the health information that enables this extended health management, especially when they are presented with information that is not culturally relevant or is language inappropriate. This study will contribute evidence to support the provision of health information to diverse Latino populations in numerous ways.

This study aims to develop and evaluate an evidence-based and culturally appropriate technology (infographics embedded in a mobile application) to facilitate HIV-related communication between Latino persons living with HIV and their clinicians. By incorporating these evidence-based infographics into an app that interfaces with EHRs both locally and globally, this work will contribute to the informatics literature regarding the effective development and implementation of SMART on FHIR apps at a global scale. Additionally, it will provide valuable information regarding the effectiveness of infographics at improving clinical communication between patients and providers, which has widespread relevance to the growing information visualization literature. Additionally, there is little in the literature regarding effective ways to tailor interventions to heterogeneous groups, as an intervention designed for one Latino group may not be relevant to others. This work will provide evidence-based guidance regarding methods to effectively tailor health related interventions to diverse Latino groups. Furthermore, this intervention is scalable and will be accessible to clinicians working with Latino patients with low health literacy in the United States and around the world.

Including an additional portion in this study to ascertain if the infographics are meaningful and acceptable to non-Latino persons with HIV will provide preliminary data about the generalizability of these infographics and set the stage for further scalability of the intervention so that more individuals in need are likely to benefit from it.

F. References

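### The design does not make the infographics the only difference between arms: treatment patients also get selected, motivational-interviewing-trained clinicians, so the claim should be limited to that package and control clinicians described

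*Combined protocol and SAP*

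**What the plan says.** Section IV.C, RCT study procedures, says standard education at each site will be evaluated before the study to "ensure the only difference between treatment and control groups is the infographic intervention". The sentence just before it sends treatment patients to interventionists and control patients to other providers.

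The treatment clinicians are described in three places:

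- **Eligibility (IV.B, RCT - Interventionists):** they are "those who have offered HIV-related care for greater than one year and are not planning to leave the clinic for the next year".
- **Selection (IV.F, sample size):** "Up to 5 interventionists at each site will be purposefully selected to participate".
- **Training and practice (IV.C, Infographic Intervention):** they are trained in MI as well as in the app and infographics, later sessions reinforce those skills, and in clinic visits "interventionists will use MI and infographics to guide education with participants".

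The Potential Risks text in IV.D calls MI a new technique for these clinicians.

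On what the trial will show, Aim 2 (section I, repeated in IV.F) is to "assess the efficacy of the intervention (infographics administered through a mobile app) as compared to standard care". The section on knowledge to be gained says "it will provide valuable information regarding the effectiveness of infographics at improving clinical communication between patients and providers".

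**The concern.** Evaluating usual education before the trial can show what control patients will receive. It cannot remove differences that the protocol itself creates between the arms, and there are two.

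The first is MI. The Background says that communication methods such as MI, "targeted at HIV self-management behaviors can help clinicians influence behavior change". By the plan's own account, MI may be an active ingredient, and it is delivered by design in one arm only.

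The second is the set of clinicians. Randomising patients balances patients. It does not balance the clinicians attached to each arm, who here are chosen by different routes.

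At stake is what a positive result means. Section III says the uncontrolled feasibility studies could not tell how much improvement was due to infographics and how much to confounders, and offers this trial as the way forward. A control group does deal with time trends and patient-level confounding. It does not separate infographics from MI or from clinician differences that are tied to arm.

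**Working it through.** **1. The arms side by side, as the protocol describes them**

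| Feature | Treatment | Control |
|---|---|---|
| Infographics in the app | Yes, at baseline, 3 and 6 months | No |
| MI training | Initial, then reinforced | None stated |
| MI used with patients | Yes, with the infographics | None stated |
| More than one year of HIV care | Required | Not stated |
| No plan to leave within a year | Required | Not stated |
| How clinicians are chosen | Purposively, up to 5 per site | Not stated |

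Only the first row is the component that Aim 2 names. The other rows may also differ by arm.

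**2. Does anything in the plan remove the other differences?**

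- Intent-to-treat analysis (IV.E) is offered against contamination. It preserves the randomised comparison of patients but leaves MI and the clinician set tied to arm.
- The primary model (IV.F) has patient random intercepts and slopes and no clinician term. Adding a clinician random effect would allow for clustering, but would not correct systematic selection or separate MI from infographics.
- Fidelity checklists on half of the intervention visits (IV.C) and the follow-up questions on interventionists' communication (D.2.3) could support exploratory comparisons within the treatment arm. Those would not be randomised, and no analysis of them is planned.

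**3. The plan's own sample-size figures reproduce**

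Inputs from IV.F: D = 0.45, correlation 0.75, 4 repeated measures, 80% power, two-sided 0.05.

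Total N = 4 × (1.960 + 0.842)² × [1 + 3 × 0.75]/4 ÷ 0.45² = 4 × 7.849 × 0.8125 ÷ 0.2025 = 125.97, so 126, or 63 per arm. With 22% attrition, 126/0.78 = 161.5, which the plan rounds up to 164. No number in the plan is disputed.

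**4. Illustration of sensitivity (the shifts are assumed, not taken from the documents)**

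Suppose the infographics have no effect, but MI, clinician differences or both shift the time-averaged outcome by b standard deviations. In SD units, the standard error of the treatment difference is √0.8125 × √(2/63) = 0.9014 × 0.1782 = 0.161. The chance of a significant main effect is 1 − Φ(1.96 − b/0.161) + Φ(−1.96 − b/0.161).

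| Assumed b | Chance of a significant result |
|---|---|
| 0 | 5% |
| 0.05 | 6% |
| 0.10 | 10% |
| 0.20 | 24% |
| 0.30 | 46% |

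If MI is counted as part of the intervention, only the clinician share of b is a distortion.

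**The case against.** The strongest reply is that MI is a declared component. The Background states that the intervention includes brief MI training, and the section headed Infographic Intervention then specifies that training and its use in visits. The phrase about the infographic intervention in the RCT procedures can be read as pointing back to that package. Testing a package against standard care is a legitimate design, and no aim promises to separate its components. This stands. It follows that MI need not contradict the statement, and a package-level result would be valid as such. What remains of the MI point is that Aim 2 and the knowledge-to-be-gained section credit infographics alone. The Potential Risks text also describes treatment patients as receiving standard care apart from infographics.

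The clinician difference is not answered by that reply, but its reach is limited. A reader might infer that the experience and tenure criteria favour the treatment arm. The documents do not support this. They say nothing about control providers' experience or turnover, some of those providers may meet the same criteria, and both sites are specialist HIV clinics, where one year of HIV care may be a low bar. Nor do the documents show how such a difference would move CD4 count, the primary outcome.

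A reader might also infer that exposure is perfectly aligned with arm. It is aligned by design, but IV.E expects that some patients may see the wrong provider, and the intervention is withheld at 9 months.

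**Conclusion.** The statement that the infographic intervention is the only difference between arms is not delivered by the design. On the package reading, MI is a matter of inconsistent definition: the trial can support a conclusion about infographics plus MI, but not about infographics alone. The clinician set is confounded with arm on either reading.

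The direction and size of any clinician effect are unknown. The probabilities above rest on assumed shifts and show only that modest differences would matter at this sample size. It would go too far to say that a positive result could be credited to nothing, or that it is biased in a known direction. The verdict assumes that control providers have no selection criteria or MI training beyond what the protocol states.

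**What to change.** **(a) Wording.** Replace the statement in the RCT procedures, and the description of the intervention in Aim 2 (both places) and in the knowledge-to-be-gained section, with *infographics delivered through the app by selected, MI-trained clinicians*. State that the trial does not isolate the infographics from MI or from clinician differences. The cost is a narrower claim.

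**(b) Control clinicians.** Where scheduling still allows, apply the same experience and tenure criteria to the providers who see control patients. The cost is a smaller pool of control providers. Otherwise, report clinician experience and turnover by arm and state the difference in clinician selection as a limit on the conclusion. That requires clinician identity to be recorded by visit.

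Drawing interventionists at random from those eligible appears too late. The trial was planned to start in January 2021, this version is dated September 2023, and the Creole usability section says interventionists have already completed the scale given at their second training session.
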